
Protocol: Pilot trial of dronabinol adjunctive treatment of agitation in Alzheimer's disease (AD) (THC-AD)

Protocol Number: IRB00052955

Protocol Version: 6.0/2July2020

There is a great need for better interventions that target Agit-AD, a major source of patient disability as well as caregiver burden and stress, particularly in the case of moderate to severe agitation. This pilot trial could open the door to “repurposing” dronabinol as a novel and safe treatment for Agit-AD with significant public health impact.

2. Specific Aims:

We propose THC-AD: a three-week placebo-controlled, double-blind, randomized clinical trial of dronabinol (10 mg QD) in 80 patients with severe Agit-AD. Concomitant medications will be limited to currently used antipsychotics, antidepressants, benzodiazepines, as well as anticonvulsant therapy when not used for seizure disorder, with lorazepam 0.75 QD total daily allowed as rescue medication, and can be administered orally or intramuscularly. Additionally, these four categories of currently used concomitant medications are permitted to be used with PRN trazodone in doses up to 100 mg total daily dose for agitation and insomnia.

AIM 1: To compare the efficacy of three weeks of dronabinol adjunctive treatment to placebo in 80 patients with severe Agit-AD.

Hypothesis 1: Compared to placebo, dronabinol treatment will be associated with a greater reduction in symptoms of agitation as measured by co-primary outcomes of a) PAS b) NPI-C Agitation, Aggression, and the sum of Agitation and Aggression. The Cohen-Mansfield Agitation Inventory will be a secondary agitation outcome. Psychosocial function, cognition, and sleep will be assessed for potential benefit.

AIM 2: To compare the safety of three weeks of dronabinol adjunctive treatment to placebo in 80 patients with severe Agit-AD.

Hypothesis 2: Dronabinol treatment will be well tolerated with (AEs) not significantly different than placebo, including incident delirium as measured by the Confusion Assessment Method (CAM).

Outcomes:

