The investigators will be blind to treatment assignment. The Research Pharmacy will prepare blind medication using opaque capsules and randomly assign eligible participants to dronabinol vs. placebo treatment. We will use minimization to ensure that treatment groups are balanced with respect to use of antidepressant and antipsychotics. This method is preferred over stratification for trials of small sample size (38). The goal is have a ratio of drug:placebo close to 1:1 but adjust over time to achieve balance of antidepressant and antipsychotic use between the dronabinol and placebo groups. To address concerns that future or past randomizations could be predicted based on knowledge of treatment assignment of any one participant (relevant to unblinding at the end of the study for ethical reasons), we will use dynamic, non-deterministic probabilities of treatment assignments (39). User-friendly software to perform this type of minimization has already been developed and used by our research group in several R01-supported clinical trials including “Pilot Trial of Carvedilol in AD” and “Venlafaxine for depression in AD”. Note that although the odds of assignment to treatment group may vary across the course of the study, treatment assignment still remains a randomized process and the investigators remain blind to treatment assignment. The Research Pharmacy will keep treatment assignment confidential but have access to treatment assignment available on a 24-hour basis. In the event of medical emergency where knowledge of treatment assignment is essential to providing safe patient care, the Research Pharmacy will inform treating physicians of the treatment assignment. The investigators will be kept blind to treatment assignment except in extreme cases. In the event of unmasking, the Research Pharmacist will make a report to the DSMB.

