Medical History	X				
Other Medications	X				
Randomization		X			
Study medication dispensing		X	X	X	
Coronavirus Impact Scale (CIS)		X			
Unblinding*					X *
Clinical Instruments					
Pittsburgh Agitation Scale (PAS)		X	X	X	X
Neuropsychiatric Inventory, Clinician Version (NPI-C)		X	X	X	X
Cohen-Mansfield Agitation Inventory (CMAI)		X	X	X	X
Modified Alzheimer's Disease Cooperative Study- Clinical Global Impression of Change (CGI-C)		X	X	X	X
Alzheimer's Disease Cooperative Study - Activities of Daily Living (ADCS-ADL)		X	X	X	X
Confusion Assessment Method (CAM)		X	X	X	X
Sleep Assessment (NPI-C Sleep Subscale)		X	X	X	X
Cognition					
SIB-8		X			X
Mini Mental State Exam (MMSE)		X			X
Drug Effect					
Drug Effect Questionnaire (DEQ)		X	X	X	X
Medication Side-Effects Questionnaire		X	X	X	X
Safety and AE monitoring					
Physical Exam	X				
Neurological Exam	X				
Vital Signs		X	X	X	X
General Medical Health Rating (GMHR)	X				
Adverse Event Monitoring		X	X	X	X
ECG		X			X
Blood draw (DNA, Biomarker, CBC, CMP, TSH)		X			X

*Only done after all other study procedures are complete

Protocol: Pilot trial of dronabinol adjunctive treatment of agitation in Alzheimer's disease (AD) (THC-AD)

Protocol Number: IRB00052955

Protocol Version: 6.0/2July2020

6. **Biostatistical Analysis:**

All analyses will be conducted using STATA (55) and R (56) under the supervision of the study statistician ([name]). Descriptive analyses will be conducted and measures checked for outliers and to ensure that distributional assumptions of the planned analyses are appropriate. If not, analogous non-parametric methods will be used. Analyses will be intent-to-treat. We expect minimal missing data, but if there is a significant amount of missing data, multiple imputation may be used if appropriate (57). To investigate sensitivity to missing values, those with and without missing values will be compared by background covariates. Tests will be two-sided and p-values <0.05 will be considered significant.

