Multiple test corrections will be applied as appropriate. All primary analyses will be adjusted for site as well as the variables balanced through minimization (use of antidepressants and use of antipsychotics). To account for the inclusion of multiple sites, we will include site as a covariate, with individuals being seen on an outpatient (largely remote) basis being treated as its own site. Secondarily, we will fit models with site, site x time, and site x treatment x time to determine if there are any effects of site on treatment effect over time. These analyses must be secondary as the study was not powered to detect these 3 way interactions. Importantly, no participants were stopped during their participation and all participants will have the same mode of assessment (either in-person or remote) throughout.

Aim 1: Efficacy will be assessed by fitting a longitudinal linear model with the co-primary outcomes (PAS and NPI-C Agitation/Aggression/Sum of Agitation and Aggression) and with time, treatment assignment and interaction between time and treatment. The latter term will be the coefficient of interest and will represent the mean difference in change over the 3-week period between the treated and placebo groups. Within-person correlations will be handled via the method of generalized estimating equations (58).

Aim 2: We will model risk of a severe adverse event as a function of treatment assignment using logistic regression, and counts of total adverse events using ordinal logistic regression or poisson regression as appropriate. We will also scrutinize counts of each specific type of AE as a function of treatment assignment to determine if there are specific adverse events which we should power ourselves to detect in future larger-scale trials. Special attention will be paid to new-onset delirium, seizures, and arrhythmias. Additionally we will specifically look at the effect of dronabinol on cognition using the SIB-8, and a regression model analogous to that in Aim 1. We will stratify adverse events by site and assess whether rates of particular AEs vary by site. In particular, we will assess whether outpatients differ in their rates and types of AEs (either favorably, due to being less acute, or unfavorably, due to a less controlled environment where falls might be more likely, for example).

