We repeated the above power analysis assuming a sample size of 60 in the event that we do not meet our original recruitment goals. With a missing data pattern that increases monotonically to 15% by week 3, with N=60, a within-person correlation of .5 and an exchangeable correlation structure we will have 80% power to detect a treatment effect of size .25, which translates to a decrease in PAS from 9.68 to 6.75 over 3 weeks; this is a 30.3% decrease. With a missing data pattern that increases monotonically to 30% by week 3, and identical conditions otherwise, we would have 80% power to detect a treatment effect of size .27, which translates to a decrease in PAS from 9.68 to 6.51 over 3 weeks; this is a 33 % decrease.

7. Risks and Discomforts:

Study medication side effects:

Based on the list of potential side effects from clinical trials with dronabinol, items will include nausea, diarrhea, dry mouth, upset stomach, vomiting, vivid or abnormal dreams, anxiety, dizziness, fatigue, confusion, depersonalization, hallucination, paranoia, depression, rapid heart rate/palpitations, flushing in the face or body, tinnitus, speech difficulty, blurred vision, headache, sweating, runny nose, and coughing.

Potential substance abuse:

Dronabinol is a Schedule III substance indicating moderate abuse liability relative to other drugs. Given the low doses to be administered, close monitoring of participants and medication administration, and relatively short duration of exposure proposed in the present study, we believe the risk of participants misusing the study medication or becoming dependent on dronabinol to be very low. Outcomes obtained from the DEQ patient-based and informant-based questionnaires will provide outcomes relevant to examining the abuse liability of the study doses in this population (e.g. subjective ratings of pleasant drug effect) that will be valuable for future studies. We will also evaluate whether participants or families of non-responders to dronabinol request to continue medication after the trial is completed.

Protocol: Pilot trial of dronabinol adjunctive treatment of agitation in Alzheimer's disease (AD) (THC-AD)

Protocol Number: IRB00052955

Protocol Version: 6.0/2July2020

Risk of Treatment Limitations:

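### Aim 2 analyses severe adverse events by logistic regression but names neither the test nor a rule for an arm with no events, and at about 40 per arm that choice can decide the safety conclusion

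*Combined protocol and SAP*

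**What the plan says.** Section 6 (Biostatistical Analysis), Aim 2, states: "We will model risk of a severe adverse event as a function of treatment assignment using logistic regression". Total adverse event counts get ordinal logistic or Poisson regression. Counts of each event type are to be examined by arm, and "Special attention will be paid to new-onset delirium, seizures, and arrhythmias", but no model is stated for those three events. The general part of section 6 adds "Tests will be two-sided and p-values <0.05 will be considered significant" and a switch to non-parametric counterparts if distributional assumptions fail. It also says "All primary analyses will be adjusted for site as well as the variables balanced through minimization", without saying whether Aim 2 counts as a primary analysis.

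Section 2 (Specific Aims) gives the purpose of Aim 2, "To compare the safety of three weeks of dronabinol adjunctive treatment to placebo in 80 patients with severe Agit-AD", and Hypothesis 2 reads "Dronabinol treatment will be well tolerated with (AEs) not significantly different than placebo". No margin or interval criterion accompanies it.

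Nowhere do the documents name a Wald, likelihood-ratio, score, exact or penalised test for severe events, or a rule for an arm with none.

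**The concern.** Severe events may be few. The case series described in section 1 reported nothing worse than mild among 40 inpatients, and this trial has about 40 per arm. If every severe event falls in one arm, treatment separates the data completely: the maximum-likelihood log odds ratio runs to infinity, its standard error grows without limit, and the Wald p-value goes to 1 however lopsided the split.

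The direction of the failure matters. Under Hypothesis 2 a non-significant result supports the favourable conclusion. The pattern that should worry readers most, with all severe events on dronabinol, is the one in which the default output shows least evidence of a difference.

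**Working it through.** **Inputs from the documents.** N=80 (section 2); allocation "The goal is have a ratio of drug:placebo close to 1:1" (section 4, Randomization and blinding), so about 40 per arm; two-sided 0.05 (section 6). A fallback of 60, about 30 per arm, appears in the power section: "We repeated the above power analysis assuming a sample size of 60". Aim 2 states no event rate, power or detectable difference, so there is no figure of the plan's own to reproduce.

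**Assumptions.** The event rates and the 6 v 0 split below are illustrations. I take severe to mean the severity grade in section 5, not the separately defined serious adverse event.

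**1. Chance of no placebo events,** (1−p)^n:

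| Assumed rate | n=40 | n=30 |
|---|---|---|
| 1% | 67% | 74% |
| 2% | 45% | 55% |
| 5% | 13% | 21% |
| 10% | 1.5% | 4.2% |

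**2. Tests at 6/40 v 0/40.**

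- Wald: the estimate does not exist, so the printed value depends on where the software stops iterating. R's glm gives log odds ratio 18.8, SE 2803, p=0.995; Python's statsmodels gives p=0.999. With site, antidepressant and antipsychotic terms added (300 simulated covariate sets), p stays at 0.993 to 0.997. Even 20 v 0 gives 0.991.
- Likelihood ratio, same model: 2[6 ln 0.15 + 34 ln 0.85 − 6 ln 0.075 − 74 ln 0.925] = 2(−16.91 + 21.31) = 8.80, p=0.003. The score test gives 0.011.
- Fisher: 2 × C(40,6)/C(80,6) = 2 × 0.0128 = 0.026.
- Firth: with one binary term this adds ½ to each cell. The odds ratio is (6.5 × 40.5)/(34.5 × 0.5) = 15.3. The penalised statistic is 2[6.5 ln(6.5/41) + 34.5 ln(34.5/41) + 0.5 ln(0.5/41) + 40.5 ln(40.5/41) − 7 ln(7/82) − 75 ln(75/82)] = 6.58, p=0.010.
- Risk difference 15%. The Wilson limits are 7.1% to 29.1% and 0% to 8.8%, so the Newcombe lower limit is 0.15 − √(0.079² + 0.088²) = 0.03 and the upper is 0.15 + 0.141 = 0.29: 3% to 29%.

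**3. How much turns on the unnamed test.**

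| Split (40 per arm) | Wald | Likelihood ratio | Fisher | Firth |
|---|---|---|---|---|
| 4 v 0 | about 1 | 0.016 | 0.116 | 0.049 |
| 5 v 0 | about 1 | 0.007 | 0.055 | 0.023 |
| 6 v 0 | about 1 | 0.003 | 0.026 | 0.010 |

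**4. Rejection rates,** by summing over every pair of binomial outcomes with 40 per arm, unadjusted, counting Wald as non-significant when an arm has no events:

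| Assumed true risks (placebo v dronabinol) | Wald | Likelihood ratio | Fisher | Firth |
|---|---|---|---|---|
| 5% v 5% | 0.05% | 9.1% | 0.4% | 3.8% |
| 10% v 10% | 1.2% | 6.5% | 1.7% | 4.5% |
| 1% v 15% | 7% | 80% | 45% | 70% |
| 2% v 15% | 11% | 67% | 36% | 57% |
| 5% v 15% | 12% | 36% | 18% | 30% |
| 10% v 25% | 37% | 44% | 33% | 43% |

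Firth's false-positive rate stayed at or below 4.5% at the common rates checked, 1% to 10%.

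**The case against.** The best defence is that the plan says logistic regression and nothing about Wald. A statistician reading the likelihood-ratio test from the same model would find p=0.003 at 6 v 0, with more power than Firth. This stands against any claim that the stated model is blind. It does not settle the matter: the likelihood-ratio test exceeds 5% false positives at common risks of 5% and 10%, and the maximum-likelihood odds ratio and its Wald interval remain unusable whichever test is chosen.

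Second, rarity is assumed. The case series lasted 7 days, was uncontrolled and had everyone on dronabinol, so it gives no placebo rate. Section 1 also reports a seizure in an earlier 15-patient crossover trial, and section 4 describes these patients as especially susceptible to adverse events. At a 10% placebo rate an empty placebo arm is very unlikely. This stands, and is why a range is given.

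Third, an absurd standard error is conspicuous, counts by event type and arm are planned, and section 9 provides unblinded review by the monitoring board. These make a misreading less likely. None replaces the stated test, and the non-parametric clause neither mentions separation nor names a substitute.

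A reader might also infer that sites without events make the treatment test fail. They do not: such a site sends only its own coefficient to infinity. In a four-site example with one empty site, the treatment estimate (log odds ratio 1.291, SE 0.650, p=0.047) was identical with that site deleted. Nor does the plan commit to a logistic model for delirium, seizures or arrhythmias.

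**Conclusion.** The concern holds in limited form. Aim 2 leaves open both the test and the handling of an empty arm, and at this sample size the choice can move p from about 1 to below 0.01 on the same data. At assumed risks of 2% v 15%, the chance of detecting the difference is 11% with Wald, 36% with Fisher and 57% with Firth.

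It is tempting to go further and say that the plan's test would return p near 1 and that the drug would be declared well tolerated. The documents do not support that. They never specify Wald, Hypothesis 2 covers adverse events generally rather than one severe-event p-value, and the planned counts by arm would also show the imbalance. What remains is a risk of misreading.

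The size rests on about 40 per arm, on assumed event rates, and on unadjusted calculations apart from the covariate check on the Wald test. This is worth correcting before unblinded analysis, because safety is one of only two aims and the remedy is cheap. It does not undermine the trial.

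**What to change.** In section 6, Aim 2, specify Firth penalised logistic regression for severe adverse events, with a penalised-likelihood test and profile-likelihood interval; if the comparison is to be unadjusted, an exact test named in advance would also serve. Report the risk difference with a 95% Newcombe or exact interval beside it. State that the same method applies to delirium, seizures or arrhythmias if any of these is formally tested, and say whether the adjustment for site and medication use extends to Aim 2.

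The cost is SAP wording. Covariate adjustment has to be limited when events are few. The choice between methods should be fixed now: at 5 v 0, Firth gives 0.023 and Fisher 0.055.

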All AEs occurring after randomization and during the 3-week treatment period, regardless of adherence to study treatment, will be recorded at all contacts. AEs will be assessed by using all available data to determine if new symptoms or medical events have occurred. A list of common side effects of dronabinol will be used to monitor for adverse events. At scheduled visits, participants and clinical staff/family caregivers will be interviewed about whether the participant experienced any symptoms or side effects on the list since the last visit. Adverse events, other than what is listed as common side effects, will still be recorded. If adverse events are noted, they will be rated as mild, moderate, or severe based on their clinical severity and frequency. Finally, medical transfers to outside general hospitals (McLean) or to a medical/surgical unit in the same hospital (Johns Hopkins and Miami Jewish Health) will be monitored. The PIs and designated study physicians will be responsible for monitoring the safety of participants. They will be responsible for appropriate medical care of participants during the study in connection with

Protocol: Pilot trial of dronabinol adjunctive treatment of agitation in Alzheimer's disease (AD) (THC-AD)
Protocol Number: IRB00052955 **Protocol Version:** 6.0/2July2020

study procedures. Safety assessments will include physical exams, vital signs, ECGs, monitoring of adverse events, and monitoring and maintenance of concurrent medication records. AEs will be reported to the local IRBs per local policy. Serious adverse events (SAEs) will be defined per FDA guidelines and reported in a timely manner as is standard in clinical trials (with the initial report being next business day). In addition, we will add the following DSMB-agreed upon SAEs to the SAE definition:

- 1) Death (already defined as an SAE per standard FDA guidelines)
- 2) Delirium at two consecutive weekly assessments
- 3) Seizures
- 4) Fall resulting in injury

In accordance to FDA reporting requirements, any serious adverse events (SAEs) that occur at Johns Hopkins, Miami Jewish Health, and McLean Hospital will be reported to Johns Hopkins and [name], M.D., the Sponsor-Investigator. Expected SAEs include delirium, intoxication, sedation, and increased appetite. Such reporting will adhere to the following process:

- 1) Sponsor-Investigator will be notified of the SAE and will be given a report

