Secondary Analyses: We will model change in additional outcomes (e.g., CMAI, MMSE, sleep, DEQ) using models analogous to that of Aim 1. We will also look at predictors of dronabinol response, including cannabinoid receptor polymorphisms and other patient characteristics. We will also model change in IL1 β , TNF α , and IL6 as a function of treatment assignment. All secondary analyses will be conducted with site as a covariate, and additional analyses which include site x treatment and site x treatment by time will be performed.

Sample size and Power analysis

Protocol: Pilot trial of dronabinol adjunctive treatment of agitation in Alzheimer's disease (AD) (THC-AD)

Protocol Number: IRB00052955

Protocol Version: 6.0/2July2020

We observed a large effect in our observational study that used PAS as outcome. PAS is one of the co-primary outcomes and we will estimate power to detect change in PAS. There are no pilot data to estimate power to detect change in NPI-C which has not been used in prior trials of dronabinol. The PAS declined in our observational study from 9.68 (3.91) pre-treatment to 5.25 (4.17) post-treatment for a treatment effect of 1.1 and 45% reduction in PAS score.

We propose to use a more conservative estimate of 30% reduction in PAS score and calculated statistical power using the formulae of Jung and Ahn (59). A 30% reduction translates to decreasing from 9.68 PAS points to 7.26 points after 3 weeks, which means a slope of -0.81 points/week. This translates to an effect size of 0.206. It is essential to account for missing data including those from dropouts. Assuming first a missing data pattern that increases monotonically to 15% by week 3, with N= 80, a within-person correlation of 0.5 and an exchangeable correlation structure, we will have 80% power to detect a treatment effect of size 0.22, which translates to a decrease in PAS from 9.68 to 7.1 over 3 weeks; this is a 26.7% decrease. Assuming next a missing data pattern that increases monotonically to 30% by week 3, then with 80 people and a within-person correlation of 0.5 and an exchangeable correlation structure, we would have 80% power to detect a treatment effect of size 0.24, which translates to a decrease in PAS from 9.68 to 6.87 over 3 weeks; this is a 29.1% decrease. Thus, THC-AD is well-powered to detect a clinically plausible and conservatively estimate decrease in PAS which is a co-primary outcome.

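### The model for total adverse-event counts has no term for time observed, so it would understate the drug:placebo ratio if early exit is more common on dronabinol

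*Combined protocol and SAP*

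**What the plan says.** Section 6, Aim 2, analyses total AEs as "counts of total adverse events using ordinal logistic regression or poisson regression as appropriate". It gives no rule for choosing between the two models, no offset or person-time denominator, and no named remedy for overdispersion.

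Other places that bear on this:

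- Section 2, Hypothesis 2: "Dronabinol treatment will be well tolerated with (AEs) not significantly different than placebo".
- Section 5, under Safety and Adverse Event (AE) monitoring, sets the collection window: "All AEs occurring after randomization and during the 3-week treatment period, regardless of adherence to study treatment, will be recorded at all contacts". It also says how events are elicited: "A list of common side effects of dronabinol will be used to monitor for adverse events".
- Section 4, Unmasking: a participant's endpoint, with unmasking, comes before Week 3 if study treatment stops early.
- Section 9, Adverse Event reporting: an AE is one of the stated reasons for discontinuing a participant from the study.
- Section 6, Sample size and Power analysis: one scenario reaches 15% missing and the next is worse, "Assuming next a missing data pattern that increases monotonically to 30% by week 3".
- Section 6, opening paragraph, for all analyses: "measures checked for outliers and to ensure that distributional assumptions of the planned analyses are appropriate". The fallback when the check fails is given next: "If not, analogous non-parametric methods will be used". The significance rule is also set there: "Tests will be two-sided and p-values <0.05 will be considered significant". The same paragraph expects little missing data and offers multiple imputation as an option, without tying it to AE counts.

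**The concern.** A count of AEs depends on how long the participant was watched. Someone who leaves after one week has had about a third of the opportunity to report events. If the AEs themselves cause the exit, the arm with more harm also has less observation, and a model of raw counts reads the lost time as fewer events. Hypothesis 2 treats the absence of a significant difference as evidence of tolerability, so an undercount on dronabinol moves the result towards the hoped-for conclusion.

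A second, separate issue concerns precision. AEs are elicited from a side-effect list at each scheduled visit, and the Medication Side-Effects Questionnaire in Section 5 names 23 items, some of them related (nausea, upset stomach, vomiting). Such counts plausibly cluster within a person. If their variance exceeds their mean, ordinary Poisson standard errors are too small.

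**Working it through.** **Plan's own figures.** The plan states no AE mean, dispersion or power, so there is no AE figure to reproduce. The 15% and 30% come from the power statement for the Pittsburgh Agitation Scale (PAS). That statement reproduces with the Jung-Ahn slope formula: for N=80, power is 81.6% at effect size 0.22 (15% missing) and 80.9% at 0.24 (30% missing), against the stated 80%.

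**Inputs from the documents.** N=80, allocation near 1:1 (40 per arm), two-sided 0.05, 3 weeks, and 15% or 30% missing by week 3.

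**Assumed inputs.** AE mean, dispersion and the split of dropout between arms. The documents give none of these.

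**Step 1: bias without an offset.** With a constant AE rate and exits spread evenly over the 3 weeks, a dropout proportion d leaves average observed time 1 − d/2. The raw count ratio is the true rate ratio times (1 − d_drug/2)/(1 − d_placebo/2).

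- 30% v 15%: 0.85/0.925 = 0.92
- 30% v 5%: 0.85/0.975 = 0.87
- 30% v 0%: 0.85/1 = 0.85
- equal dropout: 1

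If exits instead fall at the start of each week, average observed time at 30% is (0.9 + 0.8 + 0.7)/3 = 0.80, and at 15% it is (0.95 + 0.90 + 0.85)/3 = 0.90. The factors become 0.80/0.90 = 0.89 for 30% v 15% and 0.80 for 30% v 0%.

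**Step 2: simulation.** 10,000 gamma-Poisson trials per row: placebo mean 2 over 3 weeks, variance/mean of 2 in the placebo arm, true rate ratio 1.5, exit times uniform and unrelated to a participant's AE rate. The last three columns are power.

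| Dropout, drug v placebo | Ratio, no offset | Ratio, with offset | Ordinal | Robust Poisson, no offset | Robust Poisson, offset |
|---|---|---|---|---|---|
| 0% v 0% | 1.507 | 1.507 | 41.4% | 48.6% | 48.6% |
| 15% v 15% | 1.505 | 1.506 | 35.6% | 43.8% | 45.9% |
| 30% v 15% | 1.381 | 1.504 | 20.6% | 29.6% | 45.5% |
| 30% v 5% | 1.308 | 1.503 | 14.6% | 22.9% | 46.8% |
| 30% v 0% | 1.276 | 1.504 | 12.1% | 20.2% | 46.4% |

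The no-offset estimates match Step 1 (1.5 × 0.92 = 1.38; 1.5 × 0.85 = 1.28). Choosing the ordinal model does not avoid the exposure problem.

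**Step 3: overdispersion.** With no true difference, equal follow-up and variance/mean φ, the type I error of the model-based Poisson Wald test is 2[1 − Φ(1.96/√φ)].

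- φ = 1.5: 1.96/1.225 = 1.600, giving 11.0%
- φ = 2: 1.96/1.414 = 1.386, giving 16.6%
- φ = 3: 1.96/1.732 = 1.132, giving 25.8%

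Simulation at N=80 agrees (10.7–10.8%, 16.3–16.4% and 26.4%). Across all settings run at N=80, with means of 1 to 3 and φ from 1 to 4, the ordinal model held 4.5–5.4% and robust Poisson 4.6–6.2%.

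**The case against.** A reader might infer that the plan makes no allowance for overdispersion and so will produce false safety signals. The documents do not support that. Section 6 opens with a check of distributional assumptions and a non-parametric fallback. Aim 2 leaves the choice of model open and names an ordinal alternative that holds its error rate. The inflation needs three things together: Poisson is used, counts are overdispersed, and the check misses it or is not acted on. The dispersion range is assumed. A false signal would also count against tolerability, the opposite direction from the exposure bias.

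A reader might also infer that harm will be hidden. That too is conditional. The 15% and 30% are alternative whole-trial scenarios for PAS power, not a forecast for two arms, and Section 6 expects little missing data. Section 5 keeps the AE window open for 3 weeks whatever the adherence, so stopping the drug does not in itself shorten observation. Only withdrawal from the study or loss of contact does.

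A total count over a fixed window is a legitimate intent-to-treat summary when collection is complete, and an offset changes the target to a rate while observed. Total AEs are one of several safety analyses, and the data safety monitoring board (DSMB) sees unblinded data.

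These points limit the size and certainty of the concern. They do not remove it: AEs are captured only when there is contact, the documents do not say that contact continues after discontinuation from the study, and a rank-based fallback on raw counts would not correct for lost time.

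**Conclusion.** The concern holds as a conditional weakness. As written, either named model would understate AEs in an arm with more early exit. The factor on the count ratio is about 0.92 (0.89 if exits fall at the start of each week) for 30% v 15% dropout, and 0.85 (or 0.80) for 30% v 0%. It is 1 if dropout is equal. These figures assume a constant AE rate and exits unrelated to a participant's own AE rate. The direction favours Hypothesis 2.

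The overdispersion point is secondary: about 11% to 26% type I error at an assumed variance/mean of 1.5 to 3, for Poisson with model-based standard errors only.

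One matter needs reconciling whatever model is used. Section 5 records AEs over the full 3 weeks regardless of adherence, Section 4 brings the endpoint and unmasking forward when treatment stops, and Section 9 allows discontinuation from the study for an AE. Together these leave it unclear whether AE collection runs to week 3 for those who stop early. If it does so completely, observed time is nearly equal and the bias largely disappears. For a short pilot the issue is moderate and worth correcting.

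**What to change.** In Section 6, Aim 2, replace the open choice with one stated model for total AE counts: negative binomial regression, or Poisson with robust standard errors, with log days observed as an offset. Report the rate ratio with its 95% CI, and report days observed by arm.

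An offset assumes a constant AE rate, and the planned dose changes after Week 1, so add a by-week AE summary. An offset also does not fully correct the comparison if those who leave would have had more AEs than those who stay, so show exits because of AEs by arm beside the rates.

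Reconcile Section 4 (Unmasking), Section 5 (Safety and AE monitoring) and Section 9 (Adverse Event reporting) on whether AE collection continues to week 3 after early discontinuation, and define days observed accordingly.

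The cost is wording in the analysis plan and a date of last AE contact for each participant, with no new procedures. Intervals will be wider than model-based Poisson intervals if counts are overdispersed.
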